4.3.4 Clinical Studies

Infiltrating a caries lesion is a strategy to strengthen damaged tooth structure and to reduce caries progression without any surgical intervention.¹⁻³ Management of early lesions by infiltrating instead of or postponing restorative treatment would have a great impact towards improving oral health care by means of its non-invasive nature. It will drastically lengthen the life-cycle of a tooth.³ Infiltration would provide a simple and cost-effective management option with the least possible iatrogenic effect and diminished need for future re-treatment due to deteriorating of restoration margins.⁴

The promising *in vitro* results of caries infiltration on extracted teeth were underlined by different clinical trials. Several groups reported slower caries progression in infiltrated sites compared to controls: Radiographically obtained quantification reveals lesion progression in 16% of infiltrated sites compared to 53% for controls after one year and for 24% (infiltration group) and 62% (control) after two years. Recently, the three year follow-up data were published, reporting 32% progression for infiltrated lesion and 70% for controls in this split-mouth study.⁵ Meyer-Lueckel et al. measured progression rates of 7% (infiltrated sites) and 37% (controls) after 18 month in young adults.⁶ The currently available 3-year data of this study report 4% progression in infiltrated lesion and 42% for controls.⁷ Ekstrand et al. aimed to assess the efficacy of resin-infiltrated lesions covered by fluoride varnish (FV) versus FV treatment only of proximal lesions on deciduous molar teeth in a one year

split-mouth study. Radiographically, 23% of the test lesions and 62% of the control lesions had progressed, comparable to the aforementioned results in young adults.⁸

5 Device Risk Analysis and Assessment

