6.2 Specific Aimes (Primary Endpoints)

6.2.1 Specific Aim I

Significant lower rate of invasive interventions (filling) compared to standard treatment

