11.4.4 Missing Data

Missing data due to dropouts have been accounted for in adjusted sample size. The missing data will be at random.

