14.2 Withdrawal / Dropout of Subjects

Table 14.2 Withdrawal and drop-out of subjects separated by level, reason consequences

Level	Cause	Consequence
Lesion	An allocated lesion progresses radiographically into the middle or inner 1/3 of dentin (scores 4 and 5).	The lesion is treated invasively by removing the caries and placing a filling. The case is scored as "progressed" and "failure".
	The patient shows signs of reversible or irreversible pulpitis in an allocated tooth.	The tooth is treated. The case is scored as "progressed" and "failure".
Patient	The patient shows adverse reactions for one of the study materials.	Counteractive measures are taken. Unwanted effects are documented in CRF and CEF. The patient is scored as "drop out".
	The patient cannot be examined (i.e. x-ray during pregnancy)	The patient is scored as "drop out".
	One or more allocated lesions have been treated by an external dentist.	The patient is scored as "drop out".
	The patient cannot be contacted to make appointments.	The patient is scored as "drop out".
	The patient decides to withdraw his informed consent or study participation.	The patient is scored as "drop out".
Study	One or more patient(s) show severe unwanted side effects to treatment.	Individual counteractive measures are taken. The study is halted.
	More than four patients show unwanted side effects to one treatment or material used.	Individual counteractive measures are taken. The study is halted.

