18.2 Serious Adverse Events

Emergency contact details for reporting of serious adverse events are included in the CIP (Appendix A5).

Serious Adverse Events are adverse events that:

- a) led to a death,
- b) led to a serious deterioration in health that either:
 - 1) resulted in a life-threatening illness or injury, or
 - 2) resulted in a permanent impairment of a body structure or a body function, or
 - 3) required in-patient hospitalization or prolongation of existing hospitalization, or
 - 4) resulted in medical or surgical intervention to prevent life threatening illness or injury or permanent impairment to a body structure or a body function.
- c) led to fetal distress, fetal death or a congenital abnormality or birth defect.

In case of a serious adverse event and subsequent need for un-blinding the name-code list can be assessed immediately and breaking the code will not cause any further problem. The data recorded until the report of adverse event will remain included in the dataset.

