A previous infiltration study by Martignon et al. [5] reported a 3-year difference of proportions of 37.8% (95%CI: 20.5-55.2%) with (resin infiltration (68%) vs. control (30%)). Based on this and with alfa = 0.05 and a power of 80% the calculated sample size (t-test; matched pairs) would be 23 lesion pairs (thus 23 participants) to find significant differences. However, this study aimed to enroll 150 participants to not only allow for a potentially high attrition rate (20%) over a period of 3 years, but also aiming to better quantify the efficiency of the treatment effect.

Statistical Analysis

All evaluations are performed by two trained and calibrated examiners. The primary outcome is proportion of lesions that required restorative treatment (filling) after 3 years as measured via dental examination. Differences between groups will be tested using Fisher's exact test and ANOVA for Repeated Measures for subgroup analysis based on caries risk. Secondary outcomes are change in categorical lesion depth (progression to next depth category lesion; E1->E2->D1->D2->filling) after 6 months and 1, 2 and 3 years as measured by pairwise comparison of radiographs as well as the influence of Icon treatment on clinical parameters. Differences will be analyzed with McNemar's test with 95% confidence interval (95% CI) and P = .05.

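### An outside filling turns the whole patient into a drop-out although filling is the primary endpoint, and the missing-at-random statement does not fit that loss

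*Combined protocol and SAP*

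**What the plan says.** - **Primary endpoint.** Protocol 6.2.1 lists as Specific Aim I: "Significant lower rate of invasive interventions (filling) compared to standard treatment". The SAP, Statistical Analysis, states: "The primary outcome is proportion of lesions that required restorative treatment (filling) after 3 years as measured via dental examination". It adds: "Differences between groups will be tested using Fisher's exact test".
- **Filling under the study's own rule.** In the lesion-level rows of protocol Table 14.2, a study lesion that reaches the middle or inner third of dentin is handled as follows: "The lesion is treated invasively by removing the caries and placing a filling". The case is scored as progressed and as a failure.
- **Treatment by an outside dentist.** A patient-level row of the same table has the cause "One or more allocated lesions have been treated by an external dentist". The consequence is that the patient is scored as a drop-out.
- **Missing data.** Protocol 11.4.4 reads in full: "Missing data due to dropouts have been accounted for in adjusted sample size. The missing data will be at random". Section 11.2 expects about 20% loss, from 150 subjects to 120 at 3 years.
- **Retention of data.** The only stated rule for keeping data concerns serious adverse events (18.2): "The data recorded until the report of adverse event will remain included in the dataset".
- **Outside treatment is foreseen.** Sections 9.4.1 and 9.4.2 give each subject a letter asking the local dentist not to treat the study lesions before informing the investigator.

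The SAP defines no analysis set, no rule for outside fillings, no imputation and no sensitivity analysis for missing outcomes.

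**The concern.** A filling is the event that the trial counts. Under Table 14.2 the same kind of event is a lesion-level failure on one route and a patient-level drop-out on the other, depending on who placed it. Section 11.4.4 then equates drop-outs with missing data, but here the lesion's status is known, and the endpoint event itself can trigger the loss. Missing at random is an unsupported assumption for that cause, and enrolling more patients restores numbers without removing bias.

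Three further gaps add to this:

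- The rows overlap. A lesion already scored as a failure for depth may later be filled outside, and the table gives no precedence.
- The outside row concerns any treatment, which is wider than filling, and the SAP counts fillings that were required. Not every outside treatment is therefore an endpoint event.
- Section 11.4.3 has a reading code for the presence of a restoration, but does not say how it enters the primary outcome. That section is marked as revised by an amendment whose text is not shown.

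At stake are the size of the primary risk difference, the power to detect it, and an analysis decision that would otherwise be taken after the data are seen.

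**Working it through.** **The plan's own figure.** 150 × (1 − 0.20) = 120 reproduces the number in section 11.2. This allowance protects the count of pairs only.

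**Inputs.** From the documents: 120 pairs (11.2), Fisher's exact test and alpha 0.05 (SAP), and 3-year progression rates (4.3.4). Assumed, because the documents give no figures: the filling rates, the share of fillings placed outside, and two-sided testing. Two simplifications also apply: lesions within a pair are independent, and every outside filling removes its pair, which is the worst-case reading.

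**Formulas.** Let p be the true filling rate in a group and e the share of those fillings placed outside.

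- Rate seen among retained pairs: p(1 − e) / (1 − e·p)
- Expected pairs retained: 120 × (1 − e_C·p_C) × (1 − e_I·p_I), with C for control and I for Icon

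**Worked case.** Take 20% control, 5% Icon and e = 25% in both groups.

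- Control: 0.20 × 0.75 / (1 − 0.05) = 0.150 / 0.950 = 15.8%
- Icon: 0.05 × 0.75 / (1 − 0.0125) = 0.0375 / 0.9875 = 3.8%
- Difference: 12.0 points, against a true 15.0
- Pairs: 120 × 0.950 × 0.9875 = 112.6

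**Equal outside shares, 20% versus 5%.** Power is by exact enumeration, averaged over the binomial number of retained pairs. The last column treats 120 as already net of these losses.

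| Outside share | Difference (points) | Pairs retained | Fisher power | Power with 120 retained |
|---|---|---|---|---|
| 0% | 15.0 | 120 | 93.5% | 93.5% |
| 5% | 14.4 | 118.5 | 92.0% | 92.4% |
| 10% | 13.8 | 117.0 | 90.2% | 91.1% |
| 25% | 12.0 | 112.6 | 83.4% | 85.8% |
| 50% | 8.5 | 105.3 | 63.1% | 68.3% |

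If half of the outside-filled lesions had already been scored as failures and stay in, shares of 10%, 25% and 50% give 14.4, 13.5 and 12.0 points, with power of 92.0%, 89.3% and 83.4%.

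**Unequal shares, 20% versus 5%.** With 50% of control and 10% of Icon fillings outside, the rates seen are 11.1% and 4.5%, a difference of 6.6 points. With the shares reversed they are 18.4% and 2.6%, a difference of 15.8 points.

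**Lower rates.** At 10% versus 2% (true difference 8.0), equal shares of 10% and 50% give 7.3 and 4.3 points. Power is 61.3% and 28.2%, against 67.5% with none.

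**Upper range.** The progression rates in 4.3.4 are used here as if every progressed lesion were filled, which overstates filling.

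- One cited study is described as "reporting 32% progression for infiltrated lesion and 70% for controls in this split-mouth study". True difference 38.0: equal shares of 10%, 25% and 50% give 38.0, 37.5 and 34.8 points. Unequal shares of 50% control and 10% Icon give 24.1, and the reverse gives 48.7.
- The other reports 42% for controls and 4% for infiltrated lesions. True difference 38.0: the same equal shares give 35.8, 32.2 and 24.5 points.
- Power stays at 98% or more for both at equal shares.

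The difference does not always shrink. At an assumed 80% versus 50%, a 10% equal share moves it from 30.0 to 30.9 points.

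**The case against.** **Exclusion is inferred.** No passage says that a drop-out's known outcomes are discarded. A recorded filling is not missing, and both the SAP's per-lesion outcome and the restoration code in 11.4.3 ignore who placed it. This is true, and a reading that counts outside fillings is available. But 11.4.4 ties drop-outs to missing data, and the one explicit retention rule (18.2) covers only serious adverse events. Exclusion is the natural reading, and the plan has to rule it out if it is not intended.

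**An outside filling need not be one that was required.** Another dentist may intervene at a shallower depth, so leaving such fillings out can be a defensible choice of estimand. This stands in part. The documents do not give it as the reason for the rule, and the rule also discards the partner lesion and fillings that would meet the study's threshold. A sensitivity analysis deals with the threshold.

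**The effect may be small.** The letter, up to two free study restorations (6.4) and the requirement to be a regular attendee (7.2.1) should keep the outside share low. The split-mouth design and the stated blinding of patients, clinicians and evaluators make very unequal shares less likely, and nothing in the documents points to a 50%/10% split. This stands: the unequal-share figures show possible direction, not expectation, and at equal shares of 5% to 10% the loss in the 20% versus 5% example is only 0.6 to 1.2 points. None of it removes a loss that the outcome itself triggers.

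**Unseen amendments.** Two amendments are listed without their text. Nothing marks 14.2 or 11.4.4 as revised, so this is a small caveat.

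**Conclusion.** The concern holds and should be fixed. Table 14.2 as written can remove known primary-endpoint events, together with their partner lesions, and 11.4.4 supports this with an at-random statement that does not fit the cause. Confidence is high that the provisions are unreconciled; the size is unknown.

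Under the worst-case reading, with assumed rates of 20% versus 5% and equal outside shares of 5% to 50%, the difference falls by 0.6 to 6.5 points from 15.0, and Fisher power falls from 93.5% to between 92.0% and 63.1%. At low filling rates with equal shares, both effect and power fall; at high rates the difference may hold or rise. Unequal shares can bias it in either direction, though blinding within the mouth makes that less likely. Independence within pairs is not critical: with a within-pair correlation of 0.2, shares of 10%, 25% and 50% still give 13.8, 12.0 and 8.5 points, with power of 92.9%, 87.1% and 67.6% (95.5% with none).

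**What to change.** Reconcile Table 14.2, section 11.4.4 and the SAP's Statistical Analysis section:

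1. In the primary analysis, score a known outside filling of a study lesion as an event for that lesion and keep the partner lesion's data. A lesion already scored as a failure remains one. Record other outside treatment by type; it is not in itself an event.
2. Because the SAP refers to required fillings, add a sensitivity analysis that counts only outside fillings whose last study reading showed progression.
3. Replace the at-random assertion with a sensitivity analysis for pairs whose 3-year status is unknown, varying the assumed filling rate separately in each group.
4. Report the number of outside treatments per group.

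The cost is wording in three places, plus collecting the type and date of treatment from the outside dentist or at the next recall. The drawback is that some outside fillings will reflect another dentist's threshold, which item 2 tests. The change concerns scoring and data collection only and sets no treatment rule.

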14.3 Length of follow-up – Potential Study Extension

Based on the actual study design there is no extension planned. If obtained data indicate a necessity for follow-up investigations this issue will be discussed with the sponsor and documented in the study files.

15 Confirmation of Study Material Application

Application of study material will be documented in the Study Material Application form (Appendix A2) including patient ID, investigator, date of application, material batch number and signature.

16 Ethical Considerations

This protocol was approved by the IRB from the Federal University of Alabama (Appendix 3). Parents or guardians will sign an informed consent (Appendix 4). Operative dental treatment will be provided to the participants when necessary.

17 Relevant Standards and Guidelines

The Clinical Investigation Protocol for this study includes all components and documentation as required to conform to international standards for clinical research (CONSORT, ISO/DIN and Good Clinical Practice Guidelines).²⁰⁻²²

18 Adverse Events

18.1 Adverse Events

An adverse event (AE) is defined as any unintended adverse experience associated with the study materials or study procedures that results in an unplanned medical assessment or treatment, or changes the risk to subjects. Any adverse reaction to the treatment provided as part of the study will be fully investigated and reported to the IRB. AEs will be reported according to the IRB defined timelines using appropriate forms.

All materials and devices used in this study have been approved by local regulatory bodies and are currently on the market in various parts of the world. Their clinical use is according to label. Therefore, no foreseeable adverse events are expected.

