18.3 Report by the investigator to the sponsor

DMG has implemented and maintains a system to ensure that the reporting of the reportable events will be provided by the investigator to the sponsor in acceptable timely conditions using the Adverse Event/ Adverse Device Effect (AE/ADE) Report Form (Appendix A6).

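### Sections 18.1 and 18.2 admit to the AE and SAE listings only events considered associated with the study, so other events, even deaths and hospital admissions, need not be recorded.

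*Combined protocol and SAP*

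**What the plan says.** Section 18.1 defines an adverse event as "any unintended adverse experience associated with the study materials or study procedures that results in an unplanned medical assessment or treatment", and gives altered risk as an alternative consequence. It thus sets two conditions, association and consequence, and an experience must meet both to be an adverse event.

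Section 18.2 builds on this. It opens "Serious Adverse Events are adverse events that" and then lists seriousness criteria: death, life-threatening illness, permanent impairment, hospitalization, intervention to prevent these, and fetal harm.

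Section 18.1 also says "Any adverse reaction to the treatment provided as part of the study will be fully investigated and reported to the IRB", and remarks, on the ground of market approval and on-label use, that "no foreseeable adverse events are expected". Section 5.2 likewise anticipates nothing beyond acrylate allergy.

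Sections 18.3 and 18.4 set out reporting by the investigator to the sponsor and by the sponsor to the authorities. The authority limits are 2 calendar days for certain SAEs and 7 calendar days for other reportable events. Neither section defines a reportable event.

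**The concern.** The usual order is to record an untoward event first and assess its relation to the study afterwards, so that the assessment can be checked. Section 18.1 puts association into the definition. An event considered unassociated is then not a related or unrelated AE; it is not an AE at all. Because SAEs are drawn from AEs, seriousness does not bring it back.

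What is at stake is how the AE and SAE listings can be read. A low count could mean that few events occurred, or that few were considered associated, and the listings alone cannot separate the two. Nobody who works from the listings can reconsider the relatedness of an event that was never entered.

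**Working it through.** No figure in the protocol or SAP bears on this point, so there is nothing to reproduce. The check is a reading of the safety sections side by side.

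1. **Entry to the AE listing (18.1).** Association is required, and so is a consequence (an unplanned assessment or treatment, or a changed risk). The alternative of changed risk widens the second condition and leaves the first in place.

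2. **Entry to the SAE listing (18.2).** An event must be an AE and must also meet a seriousness criterion. A death or hospitalization not considered associated fails step 1, so under the text it is neither an AE nor an SAE.

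3. **Is there another place where such an event must be logged with relatedness assessed later?**
   - IRB reporting in 18.1 concerns reactions to the study treatment, which is again an attributed category.
   - Table 8.2 schedules a record of adverse effects at months 6, 12, 24 and 36. An effect is also an attributed term.
   - Table 14.2 speaks of reactions to study materials at patient level and of side effects at study level.
   - Monitoring under 12.1 checks that adverse events were reviewed and reported. That covers only what met the definition.
   - No readable section says who decides association, by what criteria, or that events judged unassociated are kept.

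4. **What is captured without attribution?**
   - Hot-cold sensitivity at every visit, and discoloration, surface integrity and secondary caries from baseline on (Table 8.2).
   - Percussion, palpation, color and hot/cold response, as secondary endpoints (6.3).
   - Post-operative sensitivity or discomfort at each recall (9.5).
   - Pulpitis in an allocated tooth, scored as progression and failure (Table 14.2).
   - Accidents, incidents and complaints, which go to the IRB under 14.1 with no association condition in the wording.

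5. **What is left uncovered?** The first four items in step 4 concern the study teeth. The fifth is a notification to the IRB and is not described as an entry in the AE or SAE data. A systemic or serious event considered unassociated has no stated place in those data.

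**The case against.** The strongest reply is that the safety picture does not rest on the AE listing alone. The tooth-level outcomes most relevant to this device are collected on schedule whatever their cause, pulpitis counts as failure with no attribution step, and 14.1 gives the IRB another route. The device is marketed, used on label and described as minimal risk. All of this stands. It limits the point to the AE and SAE listings and leaves the gap within them.

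A second reply is that the word associated is not defined and could mean associated in time, and that no section describes a causality judgement before recording. That is fair: a prior judgement is the natural reading, but it remains a reading. If a temporal sense was meant, 18.1 does not say so, and the same change of wording would settle it.

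Some stronger readings are tempting, but the documents do not support them.

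- *That blinding makes the judgement impossible.* Section 18.1 asks only about association with the study materials or procedures in general. It does not ask which material or tooth, so not knowing the allocation does not prevent recording.
- *That the AE definition distorts the Table 14.2 halt counts.* The table does not cite 18.1 and has its own attributed wording. Changing 18.1 and 18.2 would not by itself change what the table counts.
- *That the AE/ADE form proves events and device effects are merged, or that it supplies the missing relatedness field.* Its content is redacted and shows neither. In any case, a field on a form would not widen the definition in 18.1.
- *That the statement of no expected events pushes sites towards calling events unassociated.* In the text it is a statement about risk and gives no coding instruction.
- *That an upper limit on the event rate can be corrected for the omission.* This would need an assumed share of events considered associated, and the plan states no such limit to correct.

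**Conclusion.** The point holds for the AE and SAE listings. Under 18.1 and 18.2 as written, an event not considered associated is left out of both, however serious it is, and no readable section requires it to be logged for later assessment. The point does not extend to all safety data or to the claim that such events can never reach the IRB. The efficacy endpoints do not use the AE definition.

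The size cannot be stated. The documents give no expected event rate and no share of events considered associated, and any figure would come from assuming both. The conclusion assumes that associated carries its ordinary sense of a link to the materials or procedures, and that the redacted form adds no instruction that overrides 18.1. The change is worth making because it is cheap and makes the listings less dependent on prior attribution.

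**What to change.** - **18.1:** define an adverse event as any untoward event during the study, whatever its judged cause. The existing consequence threshold may be kept to limit the burden.
- **18.2:** define serious adverse events by the listed seriousness criteria alone.
- **CRF:** record relatedness (materials, procedure, neither) as a separate field, completed blind, with the assessor identified.
- **18.3 and 18.4:** state which events are reportable. Without this, the wider definition could also widen the 2-day and 7-day duties unintentionally.
- **Table 14.2:** state which recorded events the study-level halt rows count, leaving the rule itself unchanged.

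The cost is an amendment to the protocol and CRF, and more event lines over 36 months. How many more cannot be estimated from the documents; keeping the consequence threshold would hold the number down.

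If data collection is complete, the definition cannot be widened reliably after the fact. The report should then state that the AE and SAE counts include only events considered associated with the study materials or procedures.
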